6 TREATMENT PLAN

6.1 General

All patients should be registered with the Data Management Office PDMS/CORE system.

6.2 Treatment plan

Patients will receive ibrutinib orally daily for 3 cycles. Cycles will be 28 days long. Ibrutinib will be administered continuously, at approximately the same time each day, without regard to food. In the first cycle, the daily dose of ibrutinib will be 420 mg (3 capsules), in the second cycle, 280 mg (2 capsules) and in the third cycle, 140 mg (1 capsule). Patients will swallow the ibrutinib capsules whole with water without opening, breaking or chewing them.

6.3 Dose modifications

Ibrutinib therapy should be interrupted for any grade ≥ 3 non-hematologic toxicity, grade ≥ 3 neutropenia with infection or fever, or grade 4 hematologic toxicity, as assessed by the National Cancer Institute Common Terminology Criteria for Adverse Events (NCI CTCAE, version 4.03). Ibrutinib may be resumed at the starting dose for that particular cycle once the toxicity has resolved to grade ≤ 1 or baseline. If the toxicity recurs, the dose should be reduced by 1 capsule (140 mg) daily if this occurs within the first or second cycles. A second reduction of dose by 1 capsule (140 mg) daily may be made for patients in their first cycle of treatment. For patients already taking 1 capsule (140 mg) daily at the time of occurrence of the toxicity (i.e., patients in their third cycle of therapy or second cycle patients after a first dose reduction), therapy with ibrutinib should be discontinued.

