 [name]
 [name]
 [contact]
 [contact]
 Email: [contact]

For the BTK occupancy assay, peripheral blood mononuclear cells from blood collected from patients will be isolated in [name] laboratory. The frozen cell pellets then will be transported on dry ice to Pharmacyclics (at the address indicated below). All patient samples are de-identified and neither the hospital number nor the names are included. Laboratories within Pharmacyclics will analyze these samples for the BTK occupancy assay.

Pharmacyclics LLC
 [name]
 [name].

Study Calendar

	Pre- Study	Wk 1	Wk 2	Wk 3	Wk 4	Wk 5	Wk 6	Wk 7	Wk 8	Wk 9	Wk 10	Wk 11	Wk 12
Ibrutinib		A	A	A	A	A	A	A	A	A	A	A	A
Informed consent	X												
Demographics	X												
Medical history	X												
Concurrent meds	X	X-----X											
Physical exam	X				X ^f				X ^f				X ^f
Vital signs	X				X ^f				X ^f				X ^f
Height	X												
Weight	X				X ^f				X ^f				X ^f
Performance status	X				X ^f				X ^f				X ^f

CBC w/diff, plts	X				X ^f				X ^f				X ^f
Serum chemistry ^a	X				X ^f				X ^f				X ^f
Serum beta-2-microglobulin	X				X ^f				X ^f				X ^f
IgG, IgA and IgM levels	X				X ^f				X ^f				X ^f
ECG	X				X ^f				X ^f				X ^f
Adverse event evaluation		X-----X											
β-HCG	X ^b												
Urinalysis	X												
Plasma ibrutinib and chemokine levels		X ^c	X ^d		X ^e	X ^c	X ^d		X ^e	X ^c	X ^d		X ^e
BTK occupancy levels		X ^c	X ^d		X ^e	X ^c	X ^d		X ^e	X ^c	X ^d		X ^e
BTK mRNA, protein and downstream signaling		X ^c	X ^d		X ^e	X ^c	X ^d		X ^e	X ^c	X ^d		X ^e
NF-κB activation assay		X ^c	X ^d		X ^e	X ^c	X ^d		X ^e	X ^c	X ^d		X ^e
Platelet functionality assay		X ^g			X ^g	X ^g			X ^g	X ^g			X ^g

A: Ibrutinib, orally daily, 420 mg/d in cycle 1 (weeks 1-4), 280 mg/d in cycle 2 (weeks 5-8), 140 mg/d in cycle 3 (weeks 9-12).

a: Albumin, alkaline phosphatase, total, direct and indirect bilirubin, bicarbonate, BUN, calcium, chloride, creatinine, glucose, LDH, phosphorus, potassium, total protein, SGOT [AST], SGPT [ALT], sodium.

b: Serum or urine pregnancy test (women of childbearing potential).

c: On day 1 of each cycle, samples at 0 (cycle 1 only), 4, and 24 hours (see appendix C). Please note that the day 1 time zero collection in cycles 2 and 3 coincides with the day 28 24-hour collection of the previous cycles; therefore, no separate day 1 time zero collection is required in cycles 2 and 3.

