11 STATISTICAL CONSIDERATIONS

Ibrutinib is an inhibitor of Bruton's tyrosine kinase (BTK). The FDA has approved it for relapsed patients with CLL and frontline patients with del17p. Its standard dose is 420 mg/day (three 140-mg capsules). The primary objective of this pilot study is to determine the effects of different daily doses of ibrutinib (420 mg, 280 mg, 140 mg) on free drug levels in plasma, BTK occupancy by ibrutinib, BTK mRNA, BTK phospho- and total protein levels and NF- κ B activity. In total, 12 patients will be enrolled in this study. All patients will receive ibrutinib orally daily for 3 cycles. Each cycle will be 28 days long. In the first cycle, the daily dose of ibrutinib will be 420 mg (3 capsules), in the second cycle, 280 mg (2 capsules) and in the third cycle, 140 mg (1 capsule). That is, each patient will go through the three cycles with decreasing dose levels as described above. The half-life of ibrutinib is 4 to 6 hours and the drug does not accumulate after repeated oral dosing. Therefore, the influence of a previous cycle on the subsequent cycle is minimal.

Among the above pharmacokinetic and pharmacodynamic (PK/PD) parameters, a key factor is BTK occupancy. A dose level with BTK occupancy by ibrutinib $\geq 95\%$ (alternative hypothesis, H1) is regarded as sufficient, and that with an occupancy rate $< 85\%$ (null hypothesis, H0) is insufficient. Using a t-test to test H0 vs. H1, when the standard deviation of BTK occupancy rate (used as a continuous variable) is 0.10, a sample size of 10 to 12 patients can provide 80-88% power, at 2-sided significance level 0.05. This t-test will be conducted for each dose level. The data set described below shows that the standard deviation of BTK occupancy rate is about 5% when its mean is higher than 85%. As such, a sample size of 8 can provide 95% power at significance level 0.01. Therefore, even considering multiple testing adjusted by the Bonferroni method, and sample size reduction due to various reasons, this trial will still have sufficient power. An ideal dose level is sufficiently high to provide a high ($\geq 95\%$) BTK occupancy level by ibrutinib, but not higher, so that there is not much “left over drug” in plasma to cause toxicities, i.e, a low free drug level in plasma is desirable.

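### A patient reduced twice in cycle 1, to 140 mg, has no rule carrying that dose forward; read literally, cycle 2 doubles it to 280 mg

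*Combined protocol and SAP*

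**What the plan says.** Section 6.2 fixes the daily dose by cycle. Cycle 1 is 420 mg, followed by "in the second cycle, 280 mg (2 capsules) and in the third cycle, 140 mg (1 capsule"). Footnote A of the Study Calendar in Section 8 repeats this: "420 mg/d in cycle 1 (weeks 1-4), 280 mg/d in cycle 2 (weeks 5-8), 140 mg/d in cycle 3 (weeks 9-12"). Neither place makes an exception for a patient whose dose has already been reduced.

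Section 6.3 interrupts treatment for non-hematologic toxicity of grade 3 or higher, for neutropenia of grade 3 or higher with infection or fever, and for grade 4 hematologic toxicity. It then says:

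- On restarting: "Ibrutinib may be resumed at the starting dose for that particular cycle once the toxicity has resolved to grade" 1 or lower, or to baseline.
- On recurrence: "If the toxicity recurs, the dose should be reduced by 1 capsule (140 mg) daily if this occurs within the first or second cycles".
- On a further step: "A second reduction of dose by 1 capsule (140 mg) daily may be made for patients in their first cycle of treatment".
- On stopping: "For patients already taking 1 capsule (140 mg) daily at the time of occurrence of the toxicity", treatment is discontinued. The explanatory list names "patients in their third cycle of therapy or second cycle patients after a first dose reduction".

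Section 10, criterion 10.3, allows removal for unacceptable grade 3-4 toxicity despite dose optimization. Section 11 says of the BTK occupancy test: "This t-test will be conducted for each dose level".

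**The concern.** In a de-escalation design the scheduled dose usually falls at each cycle boundary, so it is easy to assume that a reduced patient can never be stepped up. The second reduction in cycle 1 breaks that assumption, because it takes the patient below the cycle 2 dose.

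Two things are at stake for that patient. The first is a return to 280 mg, the dose that led to the second reduction, where every trigger in Section 6.3 is grade 3 or higher. The second is loss of the stopping rule. A patient on 140 mg with another qualifying toxicity is to be discontinued. The same patient put back on 280 mg would instead be interrupted and resumed, or reduced.

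The restart sentence leaves a similar gap inside cycle 1, because it defines the restart dose by the cycle and not by the patient's history. A patient already down to 280 mg who then has a different qualifying toxicity may be restarted at the cycle's starting dose, which is 420 mg.

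**Working it through.** **Dose paths.** The inputs are the scheduled doses in Section 6.2 (420, 280 and 140 mg) and the reductions in Section 6.3 (140 mg each, up to two in cycle 1 and one in cycle 2).

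Dose at end of cycle = scheduled dose − 140 mg × number of reductions. Compare this with the next cycle's scheduled dose.

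| Cycle | Reductions | Dose at end of cycle | Next scheduled dose | Change |
|---|---|---|---|---|
| 1 | 0 | 420 mg | 280 mg | −140 mg |
| 1 | 1 | 280 mg | 280 mg | 0 |
| 1 | 2 | 140 mg | 280 mg | +140 mg |
| 2 | 0 | 280 mg | 140 mg | −140 mg |
| 2 | 1 | 140 mg | 140 mg | 0 |

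Only the twice-reduced cycle 1 patient goes up: 280/140 = 2.0 times the reduced dose. If the next dose were the lower of the scheduled and the reduced dose, this row would give 140 mg and no other row would change. The route within cycle 1 is 420/280 = 1.5 times the reduced dose.

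**Does any sentence prevent this?**

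- Sections 6.2, 8 (footnote A) and 11 all give the dose by cycle, without condition.
- Section 6.3 neither says that a reduction persists into the next cycle nor bars a later increase.
- The main clause of the stopping rule covers anyone on 140 mg when toxicity occurs. Its list, however, names only third-cycle patients and second-cycle patients after a first reduction. It omits a cycle 1 patient reduced to 140 mg, and a patient who would enter cycle 2 already on 140 mg.
- Criterion 10.3 can end participation but sets no dose for the next cycle.

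**Effect of a carry-forward rule on the 280 mg test.** First, the plan's own figure. Section 11 contrasts 95% with 85% occupancy, a difference of 0.10, with SD 0.10 and two-sided significance level 0.05. For a one-sample t-test, power comes from the noncentral t distribution with n − 1 degrees of freedom and noncentrality √n × (0.10/0.10) = √n.

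- n = 10: noncentrality 3.162, power 80.3%
- n = 12: noncentrality 3.464, power 88.3%

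These reproduce the stated 80-88% for 10 to 12 patients. With one patient fewer than 12:

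- n = 11: noncentrality 3.317, power 84.8%

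The plan's second scenario (SD 0.05, level 0.01) also reproduces: n = 8 gives 95.1% against the stated 95%. There, power is 99.9% with 12 patients and 99.8% with 11.

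**The case against.** The best counter-argument is that this is silence rather than an instruction. Section 6.2 is the general plan and Section 6.3 the specific section that modifies it. Section 6.3 speaks of first and second reductions and never says they lapse at a cycle boundary. An investigator could reasonably keep the patient on 140 mg, or remove the patient under criterion 10.3, for which someone with repeated severe toxicity and two reductions in 28 days is an obvious candidate.

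The route is also narrow. It takes toxicity, recovery, recurrence, a further event and an optional second reduction, all within 28 days and among 12 patients. The excess is at most one cycle at an extra 140 mg per day, at a dose below the approved 420 mg, before everyone moves to 140 mg in cycle 3. The restart at 420 mg is likewise permitted rather than required.

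Most of this stands, and it sets the severity. It does not close the gap. The 280 mg dose in cycle 2 is written without exception, the restart dose is tied to the cycle, and criterion 10.3 gives no dose. Holding the patient at 140 mg would be sound judgment, but against the schedule as printed.

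Three stronger readings are tempting, and the documents support none of them:

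- A reader might infer that patients will in fact be re-exposed. The documents give no rate for this sequence and leave room for discretion and removal.
- A reader might try to count how many more toxicities are needed before treatment stops. Section 6.3 does not say whether recurrence is counted afresh in each cycle, or exactly what triggers the second reduction, so no count is secure.
- A reader might infer that the gap requires Section 11 to specify analysis by dose actually taken. That question arises with any reduction within a cycle, whether or not doses carry forward, and is separate.

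**Conclusion.** The point holds at low severity. Read literally, Sections 6.2 and 6.3 and the Study Calendar together return a twice-reduced cycle 1 patient from 140 to 280 mg on cycle 2 day 1. That takes the patient outside the 140 mg stopping rule at the next qualifying toxicity. It is the only one of five cycle-boundary paths with an increase. Within cycle 1, the restart wording also permits 280 back to 420 mg after a different toxicity.

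The conclusion assumes that the scheduled doses apply as printed and that the optional second reduction is used. It makes no claim about frequency. It concerns patient safety and clarity of the dosing rule, and it does not call the plan's power figures into question.

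**What to change.** Add to Section 6.3: *A dose reduced for toxicity carries forward; no patient resumes treatment or starts a cycle at a daily dose above the reduced dose.* In the same section, state that the 140 mg discontinuation rule also covers cycle 1 patients reduced to 140 mg and patients carried into cycle 2 at 140 mg.

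This needs no new visits or samples. The cost is that such a patient gives no cycle 2 data at 280 mg, so the 280 mg t-test may lose that patient. The loss is not certain, because the patient took 280 mg for part of cycle 1 and a scheduled sample might fall in that window. If one patient is lost, power on the plan's main assumptions goes from 88.3% to 84.8%, a fall of 3.5 percentage points that stays within the stated 80-88%. The reduction also affects this patient's day 28 sample in the 420 mg cycle, but that already happens under the current text and is not a cost of the change.

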6.4 Missed doses

If a dose of ibrutinib is not taken at the scheduled time, it can be taken as soon as possible on the same day with a return to the normal schedule the following day. Extra capsules of ibrutinib should not be taken on the following day(s) to make up for the missed dose(s).

6.5 Duration of therapy

The duration of treatment with ibrutinib will be three 28-day cycles. Beyond this point, patients may continue to take ibrutinib at their physician-recommended dose, or switch to an alternative therapy.

6.6 Therapies prohibited during the study

Any other therapy for the treatment of CLL, including corticosteroids at doses greater than 10 mg/day of prednisone, therapeutic doses of warfarin or other anti-coagulants, strong CYP3A inhibitors or inducers.

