1.2 Endpoints

- 1.2.1 Primary: Ibrutinib plasma and chemokine concentrations, BTK occupancy by ibrutinib, BTK mRNA levels, BTK phospho- and total protein levels, downstream signaling, NF- κ B p65 levels and platelet functionality on days 1 (baseline), 8 and 28 of each cycle of treatment.
- 1.2.2 Secondary: Absolute lymphocyte count (ALC), hemoglobin and platelet levels, CLL-related symptoms, and palpable lymphadenopathy and/or hepatosplenomegaly on day 28 of each cycle of treatment; characterization of safety and tolerability of ibrutinib throughout the study.

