4.9 Warnings and precautions

Hemorrhage:

Fatal bleeding events have occurred in patients treated with ibrutinib. Grade ≥ 3 bleeding events (subdural hematoma, gastrointestinal bleeding, hematuria and post procedural hemorrhage) have occurred in up to 6% of patients. Bleeding events of any grade, including bruising and petechiae, occurred in approximately half of patients treated with ibrutinib. The mechanism for the bleeding events is not well understood. Ibrutinib may increase the risk of hemorrhage in patients receiving antiplatelet or anticoagulant therapies. Based on the risk-benefit ratio, ibrutinib is suggested to be withheld for at least 3 to 7 days pre- and post-surgery depending upon the type of surgery and the risk of bleeding.

Infections:

Fatal and non-fatal infections have occurred with ibrutinib therapy. Grade ≥ 3 infections occurred in 14% to 26% of patients. Cases of progressive multifocal leukoencephalopathy (PML) have occurred in patients treated with ibrutinib. Patients should be monitored for fever and infections and evaluated promptly.

Cytopenias:

Treatment-emergent Grade 3 or 4 cytopenias including neutropenia (range, 19 to 29%), thrombocytopenia (range, 5 to 17%), and anemia (range, 0 to 9%) occurred in patients treated with ibrutinib. Complete blood counts (CBCs) should be monitored monthly.

Atrial Fibrillation:

Atrial fibrillation and atrial flutter (range, 6 to 9%) have occurred in patients treated with ibrutinib, particularly in patients with cardiac risk factors, acute infections, and a previous history of atrial fibrillation. Patients should be clinically monitored periodically for atrial fibrillation. Patients who develop arrhythmic symptoms (e.g., palpitations, lightheadedness) or new onset dyspnea should have an electrocardiogram (ECG) performed. If atrial fibrillation persists, the risks and benefits of treatment and dose modification should be considered.

Second Primary Malignancies:

Other malignancies (range, 5 to 14%) including non-skin carcinomas (range, 1 to 3%) have occurred in patients treated with ibrutinib. The most frequent second primary malignancy was non-melanoma skin cancer (4 to 11 %).

Tumor Lysis Syndrome (TLS):

TLS has been reported with ibrutinib therapy. Patients should be monitored closely and appropriate precautions taken in patients at risk for TLS (e.g. high tumor burden).

Embryo-Fetal Toxicity:

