5.2.2 Current therapy with warfarin or other anticoagulants at therapeutic doses, e.g., low molecular weight heparin, fondaparinux, dabigatran, rivaroxaban, apixaban or edoxaban that are unable to be discontinued.

5.2.3 Active gastrointestinal conditions that are expected to impair absorption of orally administered medications.

5.2.4 Active, uncontrolled infection.

5.2.5 Inability to understand a written informed consent document.

5.2.6 Pregnancy or lactation.

5.2.7 Patients with leukemic involvement of the central nervous system.

5.2.8 Patients who currently have or have a history of the following within 6 months preceding study entry are not eligible:

- Unstable angina (UA) or myocardial infarction (MI).
- Clinically significant atrial or ventricular arrhythmias (e.g., AF, atrial flutter, ventricular tachycardia, ventricular fibrillation, or *torsades de pointes*).
- New York Heart Association (NYHA) class III or IV heart failure.

5.2.9 Patients on strong CYP3A inducers or inhibitors that are unable to be discontinued. The list of drugs that interact with cytochrome P450 enzymes can be found online at: <http://medicine.iupui.edu/clinpharm/DDIs/ClinicalTable.aspx>

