6.7 Permitted therapies

Including but not limited to hematopoietic growth factors, antimicrobials for prophylaxis or treatment of infections, allopurinol and/or rasburicase for prophylaxis or treatment of TLS.

7 **PRETREATMENT EVALUATION**

- 7.1 A complete history and physical examination including blood pressure, performance status and concomitant medications within 2 weeks prior to start of study treatment.
- 7.2 CBC and differential, albumin, alkaline phosphatase, total, direct and indirect bilirubin, bicarbonate, BUN, calcium, chloride, creatinine, glucose, LDH, phosphorus, potassium, total protein, SGPT (ALT), SGOT (AST), sodium and urinalysis within 1 week prior to start of study treatment.
- 7.3 Serum beta-2-microglobulin and immunoglobulin levels (IgG, IgA, IgM) within 1 week prior to start of study treatment.
- 7.4 Pregnancy test (blood or urine) for female patients of childbearing potential within 7 days (1 week) prior to initiation of study treatment.

- 7.5 Baseline electrocardiogram (ECG) within 1 week prior to start of study treatment.
- 7.6 Baseline bone marrow evaluation and CT scans for assessment of baseline lymphadenopathy and organomegaly are NOT required for study enrollment, but may be performed at any time as needed as standard of care tests.

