8 EVALUATION DURING STUDY

- 8.1 Physical examination along with evaluation of performance status, recording of AEs and concomitant medications on day 28 (± 2 days) of each cycle.
- 8.2 CBC and differential on day 28 (± 2 days) of each cycle.
- 8.3 Albumin, alkaline phosphatase, total, direct and indirect bilirubin, bicarbonate, BUN, calcium, chloride, creatinine, glucose, LDH, phosphorus, potassium, total protein, SGPT (ALT), SGOT (AST), and sodium on day 28 (± 2 days) of each cycle.
- 8.4 Serum beta-2-microglobulin and immunoglobulin levels (IgG, IgA, IgM) on day 28 (± 2 days) of each cycle.
- 8.5 ECG on day 28 (± 2 days) of each cycle.
- 8.6 Plasma concentrations of ibrutinib by high performance liquid chromatography with tandem mass spectrometric detection as previously described,⁶⁰ just before dosing and at 4 and 24 hours post-dosing on days 1, 8, and 28 (but before the first dose of the next cycle) of each cycle. Exception: there will be no 4-hour blood draw on day 28. Chemokines will also be measured, using enzyme-linked immunosorbent assay (ELISA).
- 8.7 BTK occupancy level by fluorescent affinity probe detection as previously described,^{9, 60} just before dosing and at 4 and 24 hours post-dosing on days 1, 8, and 28 (but before the first dose of the next cycle) of each cycle. Exception: there will be no 4-hour blood draw on day 28. See section 8.11.
- 8.8 Measurement of BTK mRNA and BTK and phospho-BTK protein and downstream signaling, as previously described,^{74, 75} just before dosing and at 4 and 24 hours post-dosing on days 1, 8, and 28 (but before the first dose of the next cycle) of each cycle. Exception: there will be no 4-hour blood draw on day 28.
- 8.9 Quantification of NF- κ B activation by ELISA as previously described,⁷⁶ just before dosing and at 4 and 24 hours post-dosing on days 1, 8, and 28 (but before the first dose of the next cycle) of each cycle. Exception: there will be no 4-hour blood draw on day 28.
- 8.10 Measurement of platelet functionality as previously described,⁷⁷ just before dosing and at 24 hours post-dosing on days 1 and 28 (but before the first dose of the next cycle) of each cycle.
- 8.11 Peripheral blood samples for plasma ibrutinib and cytokine levels, BTK occupancy, total and phospho-BTK mRNA and protein levels as well as levels of other downstream mediators of BCR signaling, and NF- κ B activity (appendix C) will be sent for processing to the laboratory of [name], Ph.D. at:

[name]
 [name]

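### Section 6.6 bars warfarin only at therapeutic doses, which is looser than the vitamin K antagonist exclusion that section 2.4 reports for later ibrutinib studies

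*Combined protocol and SAP*

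**What the plan says.** **Anticoagulants.** Section 6.6 prohibits "therapeutic doses of warfarin or other anti-coagulants, strong CYP3A inhibitors or inducers" during the study. At entry, 5.2.2 excludes "Current therapy with warfarin or other anticoagulants at therapeutic doses" when the drug cannot be stopped. Neither section defines a therapeutic dose.

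Section 2.4 describes subarachnoid hemorrhages in several warfarin-treated patients in the phase 1b-2 trial. It says these led all later ibrutinib studies to exclude concurrent oral vitamin K antagonists, and it gives no dose threshold.

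**Antiplatelet drugs.** Section 4.9 names both classes: "Ibrutinib may increase the risk of hemorrhage in patients receiving antiplatelet or anticoagulant therapies". Sections 5.2.2 and 6.6 act on anticoagulants only. The permitted list in 6.7 is open and begins "Including but not limited to hematopoietic growth factors". Antiplatelet drugs are therefore allowed by default, with no condition on starting or stopping them.

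**Platelet endpoint.** Section 1.2.1 lists "platelet functionality on days 1 (baseline), 8 and 28 of each cycle of treatment" among the primary endpoints. Study Calendar footnote g schedules one pretreatment sample and 24-hour samples on days 1 and 28 of each cycle. Appendix C gives Syk protein activation as the readout. Every patient takes 420, 280 and then 140 mg daily, in that order (6.2).

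**Medication record.** Section 7.1 collects "performance status and concomitant medications within 2 weeks prior to start of study treatment", section 8.1 requires "recording of AEs and concomitant medications on day 28" of each cycle, and the Study Calendar shows concurrent medications followed throughout treatment.

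**The concern.** A protocol's rules should be at least as strict as the safety history it cites, or say why they are not. Here the background reports a serious hemorrhage signal with one named drug and a class-wide exclusion in response. The operative rule for that same drug stops at therapeutic doses. Use below that level is left to each treating physician, in patients taking a drug that 4.9 associates with grade 3 or higher bleeding in up to 6% of patients. At stake is an avoidable safety exposure in a few patients at most.

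A second, smaller matter lies next to it. Platelet functionality is compared within patients across a fixed dose sequence with no control arm. If an antiplatelet drug is started or stopped between two samples, that change cannot be separated within the patient from the start of ibrutinib or from a dose step. Section 11 does not say how such samples would be summarized.

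**Working it through.** No figure in the plan bears on this point. The only power statement, in section 11, concerns BTK occupancy and is not affected. The main check is textual.

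**Step 1: warfarin below a therapeutic dose, section by section.**

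| Place | Below-therapeutic warfarin |
|---|---|
| 2.4 (practice reported for later studies) | Excluded; no dose limit mentioned |
| 5.2.2, dose limit applied to warfarin and other anticoagulants | Allowed at entry |
| 5.2.2, dose limit applied to other anticoagulants only | Excluded at entry if it cannot be stopped |
| 6.6 | Not prohibited on study |

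In 6.6 the dose limit stands directly before warfarin, so that section has no second reading for this drug. On the first reading of 5.2.2, both rules are looser than 2.4. On the second, a patient who could not enter on low-dose warfarin could begin it after entry. A gap remains either way, and only its width changes.

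**Step 2: what an antiplatelet change could touch (secondary point).** Counting from footnote g:

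- Samples per patient: 1 pretreatment + 3 cycles × 2 days = 7.
- Comparisons with baseline: 7 − 1 = 6.
- Same-day dose contrasts: 3 dose pairs × 2 days = 6.

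A comparison is touched when the medication change falls between its two samples. Footnote c says the day 28 24-hour draw coincides with time zero of the next cycle. Each step from that draw to the next cycle's day 1 24-hour sample is therefore about 1 day. The step from the day 1 24-hour sample to the day 28 24-hour sample is about 28 − 1 = 27 days.

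| Change falls between | Approx. days | Baseline comparisons touched (of 6) | Dose contrasts touched (of 6) |
|---|---|---|---|
| Pretreatment and cycle 1 day 1 | 1 | 6 | 0 |
| Cycle 1 day 1 and day 28 | 27 | 5 | 2 |
| Cycle 1 day 28 and cycle 2 day 1 | 1 | 4 | 4 |
| Cycle 2 day 1 and day 28 | 27 | 3 | 4 |
| Cycle 2 day 28 and cycle 3 day 1 | 1 | 2 | 4 |
| Cycle 3 day 1 and day 28 | 27 | 1 | 2 |

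Check on length: 3 × 1 + 3 × 27 = 84 days, which is three 28-day cycles. The three one-day intervals make up 3/84, or about 3.6% of the time. The row touching all six baseline comparisons needs a change within one particular day, and it touches no dose contrast. In the long intervals, a change touches 5, 3 or 1 baseline comparisons and 2, 4 or 2 dose contrasts.

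These are counts of comparisons, not of bias. The documents give neither the number of antiplatelet users nor the size of any shift in Syk activation, so no bias can be computed.

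**The case against.** **On warfarin.** The sentence in 2.4 is a one-line background summary of a cited review. The exclusion wording of the later studies is not visible, so they may have had a dose limit too. Concurrent therapy can fairly be taken to mean therapeutic use, which 6.6 does bar. The second reading of 5.2.2 may already keep every patient dependent on warfarin out at entry. What would then remain is starting low-dose warfarin within 12 weeks, a case the documents never describe. Section 4.7 also lists no contraindications. All of this stands as a limit on size. It does not explain why 6.6 carries a dose limit that the protocol's own safety history does not mention.

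**On antiplatelet drugs.** A reader might infer that unrestricted use biases a primary endpoint. The documents do not support that. Nothing in them says an antiplatelet drug shifts Syk activation. Section 11 plans descriptive summaries, calls BTK occupancy a key factor and specifies no platelet contrast, so the comparisons counted above are illustrative. Stable use would largely cancel within a patient.

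A reader might also infer from 4.9 that antiplatelet drugs should be banned, or that a stable dose for 14 days before entry should be required. Section 4.9 says only that risk may rise and calls for no exclusion. A stability rule would not lower bleeding risk, and it could delay ibrutinib in patients who, by 5.1.1, already need treatment. These objections succeed. What is left is a descriptive check on data already collected.

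**Conclusion.** The warfarin point holds as an unexplained mismatch: 6.6, and 5.2.2 on one reading, are looser than the practice reported in 2.4. It rests on taking 2.4 as written, without a dose limit. The size is small. At most 12 patients are enrolled, the number on low-dose warfarin is not given and is assumed to be low, and no hemorrhage rate can be derived for them. The case for acting is that the signal is serious and the correction costs almost nothing. It would not be right to say that the protocol lets patients take full-dose warfarin, because 6.6 prohibits that.

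The antiplatelet point is optional. A change during the study could blur some within-patient platelet comparisons, but the effect on the Syk readout is unknown and may be zero. It supports a sensitivity summary and nothing stronger.

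**What to change.** **Main change.** In 5.2.2 and 6.6, bar warfarin and other vitamin K antagonists at any dose, and keep the therapeutic-dose limit for all other anticoagulants. Word 5.2.2 so that the dose limit clearly applies only to the non-warfarin group. This takes one or two sentences in an amendment, with no new test or visit. The cost is that a rare patient on low-dose warfarin must stop it or is excluded.

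**Optional addition.** In section 11, state that the concomitant-medication record will be used to flag platelet samples that span an antiplatelet start, stop or dose change. Summarize platelet functionality once with all comparisons and once without those flagged. This needs one sentence and no new data. With 12 patients, the second summary may rest on slightly fewer comparisons.

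Do not add a stable-dose requirement for entry.
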